3.2.6 Organ Function Requirements

3.2.6.1 Adequate Bone Marrow Function Defined As:

- Peripheral absolute neutrophil count (ANC) \geq 750/ μ L
- Platelet count \geq 50,000/ μ L (transfusion independent for \geq 7 days)

3.2.6.2 Adequate Renal Function Defined As:

- Creatinine clearance or radioisotope GFR \geq 70 mL/min/1.73 m², or
- A serum creatinine based on age/gender as follows:

Age	Maximum Serum Creatinine (mg/dL)	
	Male	Female
6 months to < 1 year	0.5	0.5
1 to < 2 years	0.6	0.6
2 to < 6 years	0.8	0.8
6 to < 10 years	1	1
10 to < 13 years	1.2	1.2
13 to < 16 years	1.5	1.4
\geq 16 years	1.7	1.4

The threshold creatinine values in this Table were derived from the Schwartz formula for estimating GFR²⁷ utilizing child length and stature data published by the CDC.

Note: Patients with history of transplant associated-thrombotic microangiopathy (TA-TMA) must have a creatinine clearance or radioisotope GFR at baseline to assess renal function and must meet the above criteria.

3.2.6.3 Adequate Liver Function Defined As:

- Total bilirubin \leq 1.5 x upper limit of normal (ULN) for age, and
- SGPT (ALT) \leq 5.0 x ULN for age (\leq 225 U/L)

Note: For the purpose of this study, the ULN for SGPT (ALT) has been set to the value of 45 U/L.

3.2.6.4 Adequate Cardiac Function Defined As:

- Shortening fraction of \geq 27% by echocardiogram, or

- Ejection fraction of $\geq 50\%$ by echocardiogram or radionuclide angiogram
- 3.2.6.5 Adequate Pulmonary Function Defined As:
- Absence of dyspnea at rest
 - If pulmonary function tests (PFTs) are performed, FEV₁/FVC must be $> 60\%$
- 3.2.6.6 Central Nervous System Function Defined As:
- No clinical evidence of active CNS disease at the time of study enrollment.
 - Patients with seizure disorder may be enrolled if on non-enzyme-inducing anticonvulsants and well controlled.
 - CNS toxicity from prior therapy \leq Grade 2.

Exclusion Criteria

- 3.2.7 Patients must not have had progressive disease (PD) per the revised International Neuroblastoma Risk Criteria (INRC)²⁸ since the initial diagnosis of high-risk neuroblastoma.
Exception: Progressive disease within the first 2 cycles of Induction chemotherapy consisting of cyclophosphamide and topotecan is allowed. Patients with progression subsequent to initial cyclophosphamide and topotecan cycles are excluded.

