4.5.2 Criteria to Start ISOtretinoin – Cycles 2-5

- ALT $<$ 10 x ULN for age. For the purposes of this study, ULN for ALT is 45 U/L.
- Serum triglycerides $<$ 500 mg/dL.
- A serum creatinine based on age/gender as described in [Section 3.2.6.2](#).

Note: Observations may be obtained within 4 days prior to start of ISOtretinoin (i.e., Days 5-8 of protocol therapy).

As per [Section 5.2.8 Management of Concurrent Transplant Associated-Thrombotic Microangiopathy \(TA-TMA\)](#), ISOtretinoin may be dose-reduced or omitted per institutional practice in patients with TA-TMA.

4.5.3 Premedication and Supportive Care Recommended for the Prevention of Anticipated Toxicities Associated with Dinutuximab

Neuropathic pain, allergic reactions, and fever are commonly seen in patients receiving this antibody. Institutional guidelines for supportive care during this portion of therapy should be followed. The use of the following premedications are recommended:

- IV hydration: Administer NS 10-20 mL/kg IV over 60-90 minutes just prior to each dinutuximab infusion.
- Diphenhydramine 1 mg/kg/dose (maximum 50 mg) IV/PO 20 minutes prior to dinutuximab infusion and scheduled q6h. Hydroxyzine PO (0.5-1.0 mg/kg; max dose 50 mg) may be used instead of diphenhydramine in patients for whom there is a specific indication.

- H2 antagonist (e.g., famotidine IV dose: 0.25 mg/kg/dose every 12 hours; maximum dose: 20 mg/dose)
- Acetaminophen PO/IV: 15 mg/kg/dose (maximum 650 mg) 20 minutes prior to each dinutuximab infusion and scheduled q4-6h prn.
- Consider use of cetirizine for patients with a history of allergic reactions
- **To reduce opiate requirements during dinutuximab therapy, gabapentin dosing is recommended.** To optimize the effect of gabapentin, it should be initiated 1 week prior to expected start of antibody so that it can be increased to full dose by the start of dinutuximab administration. Dosing should follow institutional standards; however, the following dosing may be considered:
 - First day of gabapentin: 5 mg/kg/dose (max 300 mg/dose) at bedtime
 - Second day of gabapentin: 5 mg/kg/dose (max 300 mg/dose) BID
 - Third day of gabapentin: 5 mg/kg/dose (max 300 mg/dose) TID – patients should be at this dose by the time of admission for Cycle 1 dinutuximab
 - Gabapentin doses can be increased further if necessary; institutional guidelines should be followed.

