5.2.7 Isotretinoin Specific Dose Modifications

If criteria to begin a 14-day course of isotretinoin are not met by the date the therapy is due to begin, delay therapy for one week. If criteria are still not met, hold therapy until criteria are met. If an observed toxicity is possibly, probably or definitely due to isotretinoin, reduce the isotretinoin dose to 125 mg/m²/day divided BID for patients with BSA \geq 0.6 m² (for patients < 0.6 m² BSA see suggested Dose Reduction 1 in the table below). An additional dose reduction to 100 mg/m²/day divided BID for patients with BSA \geq 0.6 m² (for patients < 0.6 m² BSA see suggested Dose Reduction 2 in the table below) should occur if criteria are still not met one week after the due date for subsequent cycles and the toxicity is possibly, probably or definitely due to isotretinoin.

Note: If there is a delay in beginning isotretinoin, patients need to maintain at least one week off isotretinoin before starting the next cycle of protocol therapy). Missed doses of isotretinoin should **NOT** be made up during the one week break between the scheduled end of isotretinoin therapy and the start of chemotherapy in the subsequent cycle to avoid delays in therapy.

SUGGESTED ISOTRETINOIN DOSE REDUCTION		
BSA (m ²)	Dose Reduction 1	Dose Reduction 2
0.25-0.29	10 mg PO BID x 4 days/wk and 10 mg PO once daily x 3 days/wk	10 mg PO daily x 6 days/wk and 10 mg PO BID x 1 day/wk
0.3-0.39	20 mg PO BID x 4 days/wk and 10 mg PO BID x 3 days/wk	10 mg PO BID x 6 days/wk and 20 mg PO BID x 1 day/wk
0.4-0.49	20 mg PO BID x 5 days/wk and 30 mg PO BID x 2 days/wk	20 mg PO BID x 5 days/wk, 10 mg PO BID x 2 days/wk
0.5-0.59	30 mg PO BID	20 mg PO BID

Decrease isotretinoin dose to 125 mg/m²/day (see suggested Dose Reduction 1 in the table above for patients with BSA < 0.6 m² or reduce dose by ~25%) for subsequent cycles for the occurrence of any Grade 3 or 4 toxicities possibly, probably, or definitely attributable to isotretinoin EXCLUDING:

- Grade 3 or 4 hematologic toxicities
- Grade 3 hepatic toxicity
- Grade 3 nausea and vomiting
- Grade 3 fever

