If the same Grade 3 or 4 toxicity recurs at 125 mg/m²/day, decrease dose to 100 mg/m²/day (see suggested Dose Reduction 2 in the table above for patients with BSA < 0.6 m² or reduce dose by ~25%). If the same toxicity recurs at 100 mg/m²/day (Dose Reduction 2), discontinue isotretinoin. Patients can continue to receive protocol therapy with irinotecan, temozolomide, dinutuximab, and GM-CSF, and isotretinoin will be omitted from the remaining cycles of protocol therapy.

If serum creatinine at the time of the planned start of isotretinoin during Cycles 2-6 is > 2x baseline value documented at the start of Post-Consolidation therapy, a creatinine clearance (or nuclear medicine GFR) should be done prior to starting isotretinoin. If the creatinine clearance and/or GFR are < 50 mL/min/1.73 m², decrease the isotretinoin dose by 50%, and monitor serum creatinine twice per week. If the patient develops worsening hematuria, and/or proteinuria, hypertension, and/or a further increase in creatinine, hold isotretinoin until these parameters return to baseline levels.

If the patient develops > Grade 1 hematuria, > Grade 1 proteinuria, and/or > Grade 1 hypertension during any cycle of therapy, hold isotretinoin until these symptoms resolve or return to baseline. Please refer to [Section 5.2.8](#) for isotretinoin administration in the setting of TA-TMA.

For localized cheilitis, topical agents (e.g., Vitamin E) may be applied to lips for subsequent cycles. If this does not control symptoms sufficiently to allow oral intake, decrease the isotretinoin dose to 125 mg/m²/day for patients with BSA

$\geq 0.6 \text{ m}^2$ (for patients $< 0.6 \text{ m}^2$ BSA see suggested Dose Reduction 1 in the table above or reduce dose by ~25%).

If fasting serum triglycerides are $> 500 \text{ mg/dL}$ when isotretinoin is due to begin, hold isotretinoin and repeat fasting triglyceride level. If triglycerides remain $> 500 \text{ mg/dL}$, start medical therapy for serum triglyceride reduction and begin isotretinoin (full dose) when triglycerides are $\leq 500 \text{ mg/dL}$. If triglycerides are still $> 500 \text{ mg/dL}$ by the time the next cycle of isotretinoin is due, then reduce dose to $125 \text{ mg/m}^2/\text{day}$ for patients with BSA $\geq 0.6 \text{ m}^2$ (for patients $< 0.6 \text{ m}^2$ BSA see suggested Dose Reduction 1 in the table above or reduce dose by ~25%) for subsequent cycles.

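### At the planned isotretinoin start in Cycles 2-6, a patient with creatinine above the table and more than twice baseline, and clearance below 50, is told both to wait and to take a half dose

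*Combined protocol and SAP*

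**What the plan says.** Four places in the protocol bear on one decision, whether and how to start isotretinoin around Day 8.

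- **Sections 4.5.2 (Cycles 2-5) and 4.6.1 (Cycle 6).** Among the start criteria is "A serum creatinine based on age/gender as described in" Section 3.2.6.2. The only exception written beside these criteria is for transplant-associated thrombotic microangiopathy (TA-TMA), where Section 5.2.8 allows reduction or omission by institutional practice.
- **Section 5.2.7, opening.** A patient who misses the start criteria on the due date waits a week. After that the rule is: "If criteria are still not met, hold therapy until criteria are met".
- **Section 5.2.7, renal paragraph.** The trigger reads: "If serum creatinine at the time of the planned start of isotretinoin during Cycles 2-6 is > 2x baseline value documented". Baseline here means the value when Post-Consolidation began. The site must then measure clearance, or GFR by nuclear medicine, before giving isotretinoin. If the result is below 50 mL/min/1.73 m², the instruction is to "decrease the isotretinoin dose by 50%, and monitor serum creatinine twice per week".

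On the table itself, Section 3.2.6.2 offers it as the alternative to a clearance or GFR of at least 70 mL/min/1.73 m² and adds: "The threshold creatinine values in this Table were derived from the Schwartz formula for estimating GFR". It does not state the GFR value or the constant used.

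**The concern.** The start criteria use an absolute creatinine limit. The renal paragraph uses a limit relative to the patient's own baseline, followed by a measured clearance. Both apply at the planned start of isotretinoin, and the renal paragraph says neither that the table must also be met nor that it overrides the table. When creatinine is above the table, has more than doubled and clearance is below 50, one text withholds the drug and the other gives half of it.

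Two sites could each follow the protocol and treat the same patient state differently. The isotretinoin given, and any Grade 3 or higher events that follow from it, would then depend on which paragraph was read.

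**Working it through.** No sample size, power or alpha figure is involved, so there is no stated figure to reproduce. The check sets the rules side by side and then asks when they overlap.

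**1. Conditions for a collision.** All three must hold at the planned start in Cycles 2-6: (a) creatinine above the Section 3.2.6.2 maximum; (b) creatinine above 2 x baseline; (c) measured clearance or GFR below 50.

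| State at planned start | 4.5.2 / 4.6.1 and opening of 5.2.7 | Renal paragraph of 5.2.7 | Conflict? |
|---|---|---|---|
| (b) and (c), within the table | May start | 50% dose | No |
| (a) and (b), clearance 50 or more | Delay, then hold | Measure; no 50% step | No |
| (a), (b) and (c) | Delay, then hold | 50% dose | **Yes** |

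The measured clearance does not free the third patient from the start criterion. Sections 4.5.2 and 4.6.1 refer only to serum creatinine. If the clearance alternative of Section 3.2.6.2 were read in, it requires at least 70, which a value below 50 fails. This step needs no assumption about the table.

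**2. Examples, age 3 (maximum 0.8 mg/dL).** Assumption: 0.8 corresponds to GFR 70, so implied GFR = 70 x 0.8 / creatinine.

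- Baseline 0.5, now 1.2: 1.2/0.5 = 2.4 x baseline; above 0.8; implied GFR 56/1.2 = 46.7. Conflict, if the measured value agrees.
- Baseline 0.3, now 0.9: 3 x baseline; above 0.8; implied GFR 56/0.9 = 62.2. Hold only.
- Baseline 0.3, now 0.65: 2.2 x baseline; within the table. May start, with the half dose only if measured clearance is below 50. The rules work in sequence.

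More than doubling must exceed the maximum only if baseline is at least half of it (0.4 mg/dL at age 2 to < 6).

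**3. How much of the 50% clause is affected.** Schwartz GFR = k x height / creatinine, so at fixed height GFR and creatinine are inversely proportional. If the table maximum corresponds to GFR 70 (assumption), GFR 50 corresponds to 70/50 = 1.4 x the maximum:

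| Age (years) | Maximum, M/F (mg/dL) | Creatinine at GFR 50, M/F |
|---|---|---|
| 1 to < 2 | 0.6 / 0.6 | 0.84 / 0.84 |
| 2 to < 6 | 0.8 / 0.8 | 1.12 / 1.12 |
| 6 to < 10 | 1 / 1 | 1.40 / 1.40 |
| 10 to < 13 | 1.2 / 1.2 | 1.68 / 1.68 |
| 13 to < 16 | 1.5 / 1.4 | 2.10 / 1.96 |
| 16 and over | 1.7 / 1.4 | 2.38 / 1.96 |

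On that assumption an estimated GFR below 50 always lies above the table. The result depends on k. With assumed heights (72-90 cm in the youngest band shown, up to 155-185 cm in the oldest) and the male maxima, estimated GFR at the table limit is about 50-83 for k = 0.55 and about 38-62 for k = 0.413. For age 2 to < 6, with assumed heights of 82-118 cm:

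- k = 0.55: 0.55 x 82/0.8 = 56 to 0.55 x 118/0.8 = 81
- k = 0.413: 0.413 x 82/0.8 = 42 to 0.413 x 118/0.8 = 61

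Under the lower constant some patients within the table have an estimated GFR below 50, and for them the rules do not collide.

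**4. Size for one patient, Cycles 2-5.** The planned course is Days 8-21, 14 days. Section 4.5.7 fixes the last dose on Day 21 whatever the start date, and missed doses are not made up in the following break. If criteria are met after the one-week delay, Days 15-21 remain: 7 of 14 days. If creatinine does not recover by Day 21, 0 of 14 remain. A hold therefore loses 7 to 14 days. The renal paragraph gives 14 days at 50%. As a share of the planned full-dose course, that is 0% to 50% under the hold (taking any remaining days at full dose) against 50%. Section 4.6.4 does not repeat the Day 21 rule, so these bounds are not carried to Cycle 6.

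**The case against.** The best defence is that the rules run in order, table first and dose second. Section 5.2.7 itself opens with the hold, so a site could take the renal paragraph to apply only to patients who have passed the start criteria. That works for everyone within the table. It does not settle the case above the table, because the renal paragraph neither refers to the criteria nor excludes that patient. If the table sits near GFR 70, this reading also leaves the 50% clause with almost no one to apply to. The triglyceride paragraph of Section 5.2.7 shows the contrast: it holds the drug and resumes at 500 mg/dL or below, in line with its start criterion except at exactly 500.

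A second defence is that Section 4.5.1(e) already requires creatinine within the table to begin each of Cycles 2-5. This narrows the problem, since creatinine must cross the limit between the start of the cycle and about Day 8. It does not remove it: Section 5.2.5.4 provides for creatinine reaching twice the upper limit around dinutuximab, and Cycle 6 has no such earlier check. TA-TMA patients have their own rule.

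Four stronger readings are tempting, and the documents do not support them:

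- A reader might infer that any patient with renal decline gets contradictory instructions. Only the three conditions together produce that.
- A reader might infer that most patients due a half dose are barred. This needs a GFR value that Section 3.2.6.2 does not state, and it treats a measured clearance as if it were the Schwartz estimate.
- A reader might take none against half of the course as the usual contrast. It is the extreme, reached only if creatinine does not recover by Day 21.
- A reader might infer damage to the primary result or to an exposure analysis. Section 9.3.1 says stopping isotretinoin does not count against feasibility, and Section 9.3.4 plans no description of isotretinoin exposure.

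**Conclusion.** The contradiction stands for the patient who meets all three conditions, and for that patient it rests on the text alone. The tension is between Sections 4.5.2/4.6.1 and 5.2.7, and also between two paragraphs of 5.2.7. No precedence is stated.

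The documents give no figure for how many of the 40 evaluable patients would meet the conditions, and the number may be small. If the table corresponds to a GFR near 70, most patients who reach the 50% clause would be above the table; under a lower Schwartz constant some would be within it. For one affected cycle among Cycles 2-5, the choice is between losing 7 to 14 of 14 days and taking 14 days at half dose.

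The consequence is mainly inconsistent patient handling. The descriptive summary of Grade 3 or higher events (Aim 1.2.1, and its breakdown under Aim 1.3.1) could be affected; the primary feasibility endpoint is not directly affected. The contradiction should be removed, but it does not threaten the trial's main conclusion.

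**What to change.** Reconcile Sections 4.5.2 and 4.6.1, the opening of Section 5.2.7 and its renal paragraph, so that one rule says what happens when creatinine exceeds the Section 3.2.6.2 table and a clearance or GFR has been measured. State that rule, or a cross-reference to it, in each of these places, so that precedence is clear whichever section a site opens. Which rule applies is for the clinical team to decide.

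The cost is protocol wording in these sections. Sample size, monitoring boundaries and the primary analysis do not change.

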5.2.8 Management of Concurrent Transplant Associated-Thrombotic Microangiopathy (TA-TMA)

Isotretinoin may be dose-reduced or omitted per institutional practice in patients with TA-TMA.

5.2.9 Other Non-Hematologic Toxicities

The above sections cover dose modifications for most anticipated adverse events with this regimen. For Grade 3 or higher non-hematologic toxicities not specified above or for non-hematologic toxicities not specified above that prolong the start of subsequent cycles by ≥ 14 days, the doses of both irinotecan and temozolomide should be reduced by 25% in the subsequent cycle. If Grade 3 or higher non-hematologic toxicity recurs or cycles are again delayed by ≥ 14 days, the patient should be removed from protocol therapy.

5.2.10 Prolonged Non-Hematologic Toxicity

Patients who do not meet criteria to start the next treatment cycle (see [Section 4.5.1](#) or [Section 4.6.1](#)) within 28 days after the planned subsequent cycle start date (i.e. there is a ≥ 4 week delay in start of next cycle) due to any ongoing non-hematologic toxicity must be removed from protocol therapy.

5.3 **Inability to Tolerate Enteral Temozolomide**

For patients unable to tolerate PO temozolomide (i.e., due to nausea, vomiting), IV temozolomide may be administered.

Suggested administration schedule for chemotherapy (Days 1-5; IV temozolomide and irinotecan) and dinutuximab (Days 2-5):

- At hour 0: patient should receive IV temozolomide over 90 minutes.
- At hour 1.5 patient should start IV irinotecan over 90 minutes. On days patient is receiving dinutuximab infusion (Days 2-5 of each cycle), start IVF bolus of normal saline saline (10-20 mL/kg) over 60-90 minutes.
- At hour 3: on days patient is receiving dinutuximab infusion (Days 2-5 of each cycle), start dinutuximab infusion.
- Note: Irinotecan may be administered immediately after the completion of IV temozolomide.

Temozolomide: IV over 90 minutes daily

Days: 1-5

Dose for IV infusion: IV temozolomide may be substituted at the same dose for patients unable to tolerate enteral dosage forms. The line must be flushed before and after administration.

Sequencing: IV temozolomide may be administered immediately prior to irinotecan.

Special Precautions: IV temozolomide contains polysorbate 80, which may increase the risk of infusion or allergic reactions. If reaction occurs, premedication with diphenhydramine 1 mg/kg (maximum dose 50 mg) and hydrocortisone 2 mg/kg (maximum dose 200 mg) may be considered. Re-challenging with enteral temozolomide is also an acceptable alternative as it does not contain polysorbate 80. May be administered through the same IV line as NS. Do not administer other medications through the same IV line.

6.0 DRUG INFORMATION

See the consent document for toxicities. All other information is available on the COG website in the Commercial Agent Monographs (https://www.cogmembers.org/_files/disc/pharmacy/CommercialAgentsMonographs.pdf).

7.0 EVALUATIONS/MATERIAL AND DATA TO BE ACCESSIONED

Timing of protocol therapy administration, response assessment studies, and surgical interventions are based on schedules derived from the experimental design or on established standards of care. Minor unavoidable departures (up to 72 hours) from protocol directed therapy and/or disease evaluations (and up to 1 week for surgery) for valid clinical, patient and family logistical, or facility, procedure and/or anesthesia scheduling issues are acceptable (except where explicitly prohibited within the protocol)

7.1 End of Therapy & Follow-up

STUDIES TO BE OBTAINED	End of Therapy ¹	Time from End of Therapy (Months)													At Relapse
		3	6	9	12	15	18	24	30	36	42	48	54	60	
History	X	X	X	X	X	X	X	X	X	X	X	X	X	X	X
Physical Exam with VS (including BP)	X	X	X	X	X	X	X	X	X	X	X	X	X	X	X
Ht, Wt, BSA	X	X	X	X	X	X	X	X	X	X	X	X	X	X	X
CBC, differential, platelets	X	X	X	X	X		X	X		X		X		X	
Electrolytes including Ca ⁺⁺ , PO ₄ , Mg ⁺⁺	X	X	X	X	X		X	X		X		X		X	
Creatinine, ALT, bilirubin	X	X	X	X	X		X	X		X		X		X	
ECHO	X				X			X		X		X		X	
Cross sectional imaging of primary tumor site (MRI or CT)	X		X		X		X	X		X					X
¹²³ I-MIBG scan ²	X	X	X		X		X	X		X					X
FDG-PET scan ²	X	X	X		X		X	X		X					X
Bilateral bone marrow aspirates and biopsies	X														X
Biologic correlative studies (see Section 14.0 & Appendix X)	X														X

¹Obtain within 2 weeks of completing Cycle 6, or Cycle 5 for patients that discontinue isotretinoin.

²FDG-PET only in patients with MIBG non-avid disease at diagnosis who are followed by FDG-PET in place of ¹²³I-MIBG scan.

Note: If enrolled in APEC14B1/ANBL00B1 and consented to optional cell banking, submit PB and BM specimens if relapse occurs.

See COG Late Effects Guidelines for recommended post treatment follow-up:
<http://www-survivorshipguidelines.org/>

Note: Follow-up data are expected to be submitted per the Case Report Forms (CRFs) schedule.

7.2 Research Studies for which Patient Participation is Optional

See [Section 14.0](#) for Special Studies requirements. Required studies are detailed in [Section 14.1](#) and optional studies are detailed in [Section 14.2](#).

A summary of specimens to be collected is provided in [Appendix X](#). Every effort should be made to obtain samples from all time points, including the pre-therapy time point. However, if the pre-ANBL19P1 therapy sample cannot be obtained, subsequent samples should still be collected as specified.

